The specific aims of the study are:

- 1) Determine the proportion of university students who will utilize online psychological interventions for symptoms of depression and anxiety.
- 2) Determine if a 10-week online group CBT (GCBT) intervention effectively reduces symptoms of depression and anxiety among university students when compared with three control group interventions (i.e., Mood Flow, SilverCloud guided, and SilverCloud unguided).

This is a parallel group, unblinded randomized controlled trial (RCT), to assess the effectiveness of a novel 10-week online group CBT (GCBT) intervention that we have developed for university students reporting symptoms of depression or anxiety.

Students will be recruited from Stellenbosch University to participate in this RCT. Students will be sent an email invitation in randomized batches of 400 students at a time. The email will explain that we are conducting research on the use of digital interventions to reduce symptoms of depression and anxiety. The email will also invite students to enrol in the study by completing an online baseline assessment. Students will be asked to complete an Informed Consent Form before participating in the baseline assessment or any of the interventions. The Online Informed Consent Form outlines the primary aims of the study, inclusion/exclusion criteria, and rights as a participant (e.g., skip any question, discontinue at any time, right to withdraw) as well as detail about the online psychological group interventions. Students who meet the inclusion criteria will be randomized in a 1:1 ratio to one of the four study arms: the experiment group (i.e., the 10-week online GCBT intervention) or one of the three control groups (i.e., Mood Flow, SilverCloud guided, and SilverCloud unguided). We will repeat this recruitment strategy until we reach our target sample size of at least 400 students (i.e., a minimum of 100 students per intervention arm).

Students who enrol in the study will complete a baseline assessment prior to randomization. Follow-up assessments will also be conducted at 3-months, 6-months and 12-months post intervention. Assessment will consist of online self-report questionnaires administered using Qualtrics^{xM} software to record the following:

- (a) Respondent contact information
- (b) Background information

- (c) COVID-19
- (d) Physical health
- (e) Attention and concentration
- (f) Substance use
- (g) Symptoms of depression
- (h) Worry and anxiety

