Sessions will be facilitated by registered counsellors (the equivalent of psychological technicians with four years of university training) and registered psychologists. A facilitators' handbook, with detailed descriptions of the content of each session and facilitation guidelines will be provided and facilitators will be trained on group therapy facilitation. Online sessions will be recorded so that they could be reviewed during supervision.

Control groups:

The control groups will be directed to make use of one of three digital applications (apps); i.e., Mood Flow, SilverCloud (guided), and SilverCloud (unguided).

Assessment schedule:

As part of the study, the experimental group intervention participants will complete a baseline assessment at the start of the study and process assessments every two weeks. Follow-up assessment will also be administered to monitor symptom change (i.e., 3-month post-treatment, 6-month post-treatment, and 1-year post-treatment). The control group will only complete the baseline assessment and a 3-month follow up assessment.

Management of risk

If during the initial screening and recruitment or follow-up assessments, any participant endorses a "2" (more than half the days) or "3" (nearly every day) on the PHQ-9 (Thoughts that you would be better off dead or of hurting yourself in some way), they will receive an automated message that provides a list of emergency resources. The email and text message will be sent immediately after endorsing the item. Students who report active suicidality with intent at any time during the study will be referred to appropriate campus-based crises services, and national suicide helplines.

Statistical Analyses:

Data will be cleaned and analysed with SPSS (version 27). Descriptive statistics will be used to summarise participant characteristics, attendance rates, and primary outcomes.

We will evaluate aggregate intervention effects, as well as evaluate aggregate

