differences across arms using conventional intent to treat (Gupta, 2011) and complier average causal effect (CACE) (Angrist, Imbens, & Rubin, 1996) analyses based on inverse probability weights to deal with loss to follow-up (Robins, Rotnitzky, & Zhao, 1994). Log-binomial regression will be used to estimate remission and to report adjusted prevalence ratios with 95% CIs. If convergence problems occur, we will fall back on Poisson regression with robust variance estimation. We will calculate numbers needed to treat for each outcome (remission of anxiety, depression, and combined PHQ-ADS). To estimate CACE, we will use two-stage least squares (Wooldridge, 2020) and control function procedures (Clarke & Windmeijer, 2012). We will evaluate the validity of the assumptions needed for this estimation and conduct sensitivity analyses. Distributions and correlates of dropout and missing data will be provided in reports.

Process analyses will allow us to investigate the pathways through which the intervention affects the outcomes by investigating intermediate effects of the individual intervention rule (IIR) in predicting responses in the five-minute process assessments that will be carried out every two weeks with students in the intervention arm over the 10 weeks of the intervention. The instrument used in these process assessments, the CBRSS (Miner, Schueller, Lattie, & Mohr, 2015), measures frequency of applying core cognitive skills (CSF) and core behavioral skills (BSF) during times of stress. We will also use the 4-item screening version of the GAD-7 and PHQ-9, the PHQ-4 (Kroenke, Spitzer, Williams, & Löwe, 2009), to assess anxiety-depression over each 2-week period. We will begin by investigating associations of the CSF and BSF measures both cross-sectionally and with a 2-week time-lag in predicting PHQ-9 scores. Our interest will be in determining whether CSF and BSF predictor PHQ-9 scores and if these associations increase over time.

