We will also be interested in the associations of CSF and BSF data and individual differences in the slopes of PHQ-4 scores on CSF and BSF with the outcomes at the end of the intervention and in the 3-month, and 6-month follow-ups (i.e., academic attrition, performance, and engagement along with diagnostic classifications based on the GAD-7, PHQ-9, and PCL). We will also be interested in individual differences in mean values of CSF and BSF over the course of the intervention, changes (i.e., stronger changes in CSF and BSF over time for some students than others), and slopes of PHQ-9 scores on CSF and BSF scores in predicting long-term outcomes. We will be especially interested in the possibility of nonlinearities that document the existence of important minimum engagement

thresholds for achieving treatment effects (Chien et al., 2020). We will use a multilevel modelling framework to carry out these analyses. Finally, we will be interested in the extent to which the association of the IIR scores with long-term outcomes are mediated by the process measures obtained in the process assessments collected every two-weeks.

ETHICAL CONSIDERATIONS

Consent:

Eligible participants who satisfy the inclusion criteria and do not meet the exclusion criteria outlined in this proposal will be invited to participate in the online psychological group interventions and will be provided with an Online Informed Consent Form on participation in the research and online group intervention. The Online Consent Form outline: (a) aim of the research study, (b) risks and benefits of the research study, (c) assurance of confidentiality, (d) rights as a participant, including the right to refuse to answer any question, discontinue participation at any time, and withdraw from the study and (e) details on participating in online group interventions. No information obtained will be used without receiving the completed Informed Consent Form. After completing the consent form, participants will be emailed a pdf copy of the Informed Consent Form for their records.

Potential risks:

(a) *Privacy*. Participants who provided informed consent will be given details on the online intervention groups that they have been randomized to. Respective group facilitators will make a note of which students join which session as an online form of a register. Each participant will be assigned an alphanumeric ID so that data is stored in a way that is not directly linked to any identifying information.

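### No pre-intervention CBRSS score is planned, so the level-based process analyses cannot separate skills that students brought from skills they gained

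*Combined protocol and SAP*

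**What the plan says.** The combined protocol and SAP introduces the scale under Statistical Analyses as "The instrument used in these process assessments, the CBRSS", and says that it "measures frequency of applying core cognitive skills (CSF) and core behavioral skills (BSF) during times of stress". Those assessments "will be carried out every two weeks with students in the intervention arm over the 10 weeks of the intervention".

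Under Assessment schedule, GCBT participants "will complete a baseline assessment at the start of the study and process assessments every two weeks", so the baseline and the process surveys are separate items. For the comparators: "The control group will only complete the baseline assessment and a 3-month follow up assessment".

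The METHODS section places the baseline before allocation: "Students who enrol in the study will complete a baseline assessment prior to randomization". Its topics, (a) to (w), include depression and anxiety but nothing on coping or use of cognitive and behavioural skills.

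The stated purpose of the process analyses is to study pathways from intervention to outcome. Several uses of CSF and BSF are planned:
- Cross-sectional and two-week-lagged associations with PHQ-9.
- Level as a predictor of long-term outcomes: "We will also be interested in individual differences in mean values of CSF and BSF over the course of the intervention".
- Change in CSF and BSF over time, and slopes of PHQ scores on them.
- A search for minimum engagement thresholds.
- Mediation of the association between IIR scores and long-term outcomes.

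The models are multilevel. No adjustment for an earlier skill level is stated.

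**The concern.** A student's mean skill use during treatment is the skill brought to the trial plus the skill gained in it. Students who already cope well may have fewer symptoms later whatever GCBT does. Without a pre-treatment score, an association between mean CSF or BSF and outcome may reflect only that prior difference. A threshold in skill use may likewise mark who was coping well at the start.

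Symptoms do not have this gap, because depression and anxiety are baseline topics. The proposed mechanism is the quantity with no starting value. At stake is whether the process results can say anything about acquired skill. The comparison between arms is not at stake.

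**Working it through.** The plan gives no figure on this point, so there is none to reproduce. What follows is an illustration.

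**Inputs from the documents.** At least 400 students in four arms, 400/4 = 100 in GCBT. One survey per two weeks over 10 weeks, 10/2 = about 5 waves. Ten workshops in five themes of two.

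**Assumptions (not in the documents).** Prior skill S0 has variance 1. Gain G has SD 0.5 or 1.0, is independent of S0 and accrues linearly, so wave k = S0 + G·k/5 + error. Reliability is 0.8, so error variance is 1/0.8 - 1 = 0.25. The outcome Y has variance 1, correlates -ρ with S0 (ρ = 0.2 or 0.3) and does not depend on G. Any association with Y beyond chance is therefore due to prior skill.

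**1. Mean CSF, unadjusted.** The average of k/5 over five waves is 0.6. Hence Var(M) = 1 + 0.36·SD² + 0.25/5 and corr(M,Y) = -ρ/√Var(M). Probability of significance at two-sided 5% ≈ Φ(atanh|r|·√97 - 1.96).

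For ρ = 0.3 and SD 0.5: Var(M) = 1 + 0.09 + 0.05 = 1.14; r = -0.3/1.068 = -0.28; 0.289 × 9.85 = 2.84; Φ(0.88) = 81%.

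**2. Adjusted for one baseline score B = S0 + error.** r(B,Y) = -ρ/√1.25 and r(M,B) = 1/√(1.25·Var(M)). The partial correlation is [r(M,Y) - r(B,Y)·r(M,B)] / √[(1 - r(B,Y)²)(1 - r(M,B)²)], tested with √96.

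Same case: r(B,Y) = -0.268 and r(M,B) = 0.838; (-0.281 + 0.225)/(0.963 × 0.546) = -0.107; 0.107 × 9.80 = 1.05; Φ(-0.91) = 18%.

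**3. Mean of waves 2 to 5, adjusted for wave 1.** Same partial formula with Var(wave 1) = 1.25 + 0.04·SD², Var(mean) = 1 + 0.49·SD² + 0.25/4 and covariance 1 + 0.14·SD².

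**4. Change, wave 5 minus wave 1.** S0 cancels, so the correlation with Y is 0 and rejection is nominal.

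| ρ | SD of gain | corr(M,Y) | Unadjusted | Adjusted for baseline | Adjusted for wave 1 | Change |
|---|---|---|---|---|---|---|
| 0.2 | 0.5 | -0.19 | 46% | 11% | 9% | 5% |
| 0.2 | 1.0 | -0.17 | 39% | 8% | 6% | 5% |
| 0.3 | 0.5 | -0.28 | 81% | 18% | 16% | 5% |
| 0.3 | 1.0 | -0.25 | 72% | 12% | 8% | 5% |

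Monte Carlo runs of the same model (2,000 per setting) agree: about 38% to 84% unadjusted, 7% to 19% with a baseline score, 6% to 17% with wave 1, and 5% to 6% for change. The excess that remains after adjustment comes from measurement error in the single score.

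**5. A second model.** Let GCBT change no skill at all, let waves have intraclass correlation 0.5 to 0.9, and let stable skill correlate r = 0.2 to 0.4 in size with outcome. The five-wave mean then correlates r·√(5·ICC/(1 + 4·ICC)) = 0.18 to 0.40 with outcome and is significant in 44% to 98% of trials. One baseline score lowers the correlation to 0.06 to 0.25.

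**6. Gain before the first wave.** If that wave is at week 2 (assumed), up to two workshops, one theme of five, have been given. With linear gain 2/10 = 20% is unobserved. If gain follows 1 - exp(-t/τ), change from week 2 to week 10 captures 36% (τ = 2 weeks) or 57% (τ = 4 weeks), so 64% or 43% is missed.

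**The case against.** The strongest reply is that most of the false-positive problem can be handled with the waves already planned. The plan includes within-student change, two-week lags and multilevel models, and a stable prior level largely drops out of change terms. Adjusting later waves for the first one does about as well as a baseline score. This stands, under the assumptions that gain is linear and independent of prior skill. It limits the problem to the level-based analyses. What only a baseline score recovers is gain before the first wave.

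A reader might infer that the trial will credit prior skills to GCBT. The documents do not say so. They speak of associations and prediction, and the only mediation named concerns IIR scores, not arm. The supportable statement is that the level analyses cannot distinguish the two sources.

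Covariates for the process models are unspecified, and baseline symptoms will be available. If prior skill acts only through baseline symptoms (assumed), adjusting for one symptom score lowers rejection from 45%-82% to 6%-8%. A direct path would leave more. This is a fair mitigation, but the plan does not state it.

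The first wave is undated and the baseline list gives topics, not instruments, so a CBRSS before the first workshop is not strictly excluded. It is not the natural reading, and if it is intended the plan should say so.

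Finally, neither study aim mentions mechanism, so these analyses are secondary. That also stands.

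**Conclusion.** The concern holds in a limited form. On the natural reading, no CBRSS score precedes the intervention, and analyses of mean CSF/BSF, cross-sectional association and thresholds cannot separate prior from acquired skill. With assumed prior-skill correlations of -0.2 to -0.3 with outcome, 100 students, five waves and reliability 0.8, mean CSF is significant in about 40% to 80% of trials in which skill gain does nothing. One baseline score brings this to about 7% to 19%, which is a large reduction but not a cure.

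The change analyses are sound on this point but start late. They lose about 20% of the gain if it is linear and the first wave is at week 2, and more if learning is early.

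A baseline score would not by itself show that GCBT produced the skills, because the control arms never complete the scale. The ITT and CACE comparisons are untouched. This is a cheap improvement to secondary analyses and does not threaten the trial's main result.

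**What to change.** 1. Add the CBRSS to the pre-randomisation baseline questionnaire in all four arms.
2. Add it to the 3-month assessment, which all arms already complete, so that skill change can be compared between GCBT and controls.
3. State when the first process wave takes place relative to the first workshop.
4. In the SAP, adjust every CSF/BSF level analysis for the baseline score and report change from baseline.
5. For students without a baseline score, adjust for the first wave and describe the results as associations.

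The cost is one scale, taken from a process survey described as lasting five minutes, added twice to existing online questionnaires, plus SAP wording. Students bear a few more minutes of questionnaire time. Those already enrolled would lack the score, so the change is worth most if made early.

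### GAD-7 and PCL classifications are planned at the end of the GCBT intervention but not collected then, the PHQ-9 one is in doubt, and the app arms' 3-month follow-up has no defined origin

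*Combined protocol and SAP*

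**What the plan says.** All references are to the combined protocol and SAP.

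- **Outcomes wanted.** In Statistical Analyses, the process-analysis paragraphs link the cognitive and behavioural skill measures (CSF, BSF) and individual PHQ-4 slopes to "outcomes at the end of the intervention and in the 3-month, and 6-month follow-ups". The outcomes listed there are academic attrition, performance and engagement, together with "diagnostic classifications based on the GAD-7, PHQ-9, and PCL".
- **General schedule.** The text under Study aims describes a baseline assessment before randomisation and then states: "Follow-up assessments will also be conducted at 3-months, 6-months and 12-months post intervention". It makes no distinction between arms.
- **Schedule by arm.** Under Assessment schedule, GCBT students complete a "baseline assessment at the start of the study and process assessments every two weeks", followed by follow-ups at "3-month post-treatment, 6-month post-treatment, and 1-year post-treatment". For the three app arms: "The control group will only complete the baseline assessment and a 3-month follow up assessment".
- **Process survey.** Statistical Analyses describes "five-minute process assessments that will be carried out every two weeks with students in the intervention arm over the 10 weeks of the intervention". The instruments named for it are the CBRSS and the PHQ-4, the latter introduced as a 4-item screening version of the GAD-7 and PHQ-9.
- **Conflicting wording.** The same paragraphs also plan to predict PHQ-9 scores at a two-week lag and to use slopes of PHQ-9 scores on CSF and BSF.

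**The concern.** The analysis text names an outcome time that the assessment schedule does not serve. If the schedule is followed as written, the GCBT arm reaches week 10 with a skills scale and four symptom items, and the planned diagnostic classifications at that time cannot be formed. Week-10 symptom status cannot be recovered later, so the gap has to be closed before data collection or the commitment withdrawn.

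A second timing question affects the between-arm comparison in Aim 2. Under Assessment schedule, 3 months is the only time after baseline at which all four arms are assessed. The GCBT programme has a defined length of 10 weeks; no duration or end of use is given for Mood Flow or either form of SilverCloud. A follow-up counted from the end of the intervention therefore has a date in one arm and none in the other three. If the arms were measured at different times since baseline, elapsed time would be confounded with arm.

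**Working it through.** The plan gives no figure of its own to reproduce. The check sets each scheduled assessment against the outcome times and scales that the process analyses require.

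**Inputs.** GCBT length: 10 weeks (Study aims and the GCBT description). Follow-ups: 3, 6 and 12 months after treatment for GCBT, and 3 months only for the app arms (Assessment schedule). Process survey: every two weeks, GCBT only, CBRSS and PHQ-4 (Statistical Analyses). Assumptions: 3 months is about 13 weeks, and the first process survey falls at week 2.

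**Step 1: calendar for the GCBT arm, in weeks from the start of treatment.**

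- Process surveys: weeks 2, 4, 6, 8, 10.
- 3-month follow-up: 10 + 13 = week 23.
- 6-month follow-up: 10 + 26 = week 36.
- 12-month follow-up: 10 + 52 = week 62.

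**Step 2: needed against collected, GCBT arm.**

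| Outcome | End of intervention (week 10) | 3 months (week 23) | 6 months (week 36) |
|---|---|---|---|
| GAD-7 classification | Not collected; PHQ-4 only | Possible | Possible |
| PCL classification | Not collected; no PCL item named | Possible | Possible |
| PHQ-9 classification | In doubt; PHQ-4 is the named instrument, but PHQ-9 scores are referred to | Possible | Possible |
| Academic outcomes | Not affected by this argument | Not affected | Not affected |

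Possible means that the follow-up questionnaire is scheduled then and can yield the classification if it contains the scale. The questionnaire is listed by domain rather than by instrument, so this is an assumption.

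**Step 3: can another assessment stand in at week 10?** The last process survey cannot: four screening items do not give a full-scale GAD-7 classification, and they include nothing for the PCL. The 3-month assessment cannot either: the analysis text lists it separately from the end of the intervention, and the schedule places it about 23 - 10 = 13 weeks later.

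**Step 4: the PHQ-9 wording.** Lagged PHQ-9 scores and PHQ-9 slopes, read literally, need repeated PHQ-9 data during treatment. The named survey instrument is the PHQ-4. Either the PHQ-9 is meant to be in the two-weekly survey and is missing from its description, or PHQ-4 was meant. On the first reading the PHQ-9 classification could be formed near week 10; on the second it could not. The GAD-7 and PCL results are the same on both.

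**Step 5: origin of the 3-month assessment.**

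- GCBT: about week 23, as above.
- App arms, counted from the end of the intervention: no date can be derived, because no end is stated. It would be about week 23 if a notional 10-week period were applied to them.
- App arms, counted from baseline: about week 13.
- Conditional worst case of these two counts: 23 - 13 = 10 weeks' difference, taking baseline and the start of treatment as close together.

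**The case against.** The strongest reply is one of scope. The sentence belongs to process analyses whose predictors exist only in the GCBT arm, and it is introduced as something of further interest. The intention-to-treat, complier-average and number-needed-to-treat analyses nowhere refer to an end-of-intervention time. All of this stands: the missing classifications concern the GCBT arm, not all of the roughly 400 students, and Aim 2 does not rest on them.

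A reader might infer that a whole named outcome is lost. The documents do not support that. Academic outcomes in the same sentence do not need these scales, and the 3- and 6-month classifications remain possible. Nor can it be said that no symptom scale is planned around week 10, since the references to lagged PHQ-9 scores and PHQ-9 slopes point the other way. Those references leave the PHQ-9 unresolved but do nothing for the GAD-7 or PCL.

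A reader might also fault the trial for having no four-arm comparison at week 10. The plan promises none, and comparing arms 3 months after treatment is a legitimate choice.

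On timing, the text under Study aims counts follow-up from the end of the intervention for enrolled students generally, and the shorter wording for the app arms under Assessment schedule need not change that origin. It would therefore be wrong to assert that the arms will be measured 10 weeks apart, or that natural recovery will produce an apparent effect; the documents give neither a from-baseline count nor a recovery rate. What remains is that the end of the intervention is undefined for the app arms.

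**Conclusion.** The point holds in two limited parts.

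1. **A contradiction between analysis and schedule.** In the GCBT arm (at least 100 students), the GAD-7 and PCL classifications planned at the end of the intervention cannot be computed from the assessments described. Whether the PHQ-9 classification can be computed depends on which of two conflicting descriptions is intended. The contradiction affects one time point of one group of outcomes in a single-arm process analysis. It rests on the process survey containing only the instruments named for it, and on there being no unlisted assessment at week 10.

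2. **An undefined origin.** The only time after baseline shared by all four arms under Assessment schedule has no defined start of counting in three of them. The size of any mismatch is unknown. A count from baseline, which the documents neither state nor rule out, would set about week 13 in the app arms against about week 23 in GCBT; a common origin and interval would remove the difference.

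Both should be settled before data collection. Neither invalidates the main comparison if the 3-month assessment is dated alike in all arms.

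**What to change.** **End-of-intervention outcomes.** Choose one:

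- Add the full PHQ-9, GAD-7 and PCL to the week-10 online survey in the GCBT arm and enter this in Assessment schedule. The cost is a few more minutes of respondent time, once. Extending it to the app arms is optional and would add a wave for students now asked for only two assessments.
- Remove the end-of-intervention time point for these three classifications only, keeping it for the academic outcomes. The cost is one qualified phrase and the loss of symptom classifications at that time.

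**PHQ-4 and PHQ-9.** State which scale is collected every two weeks, and use that name throughout the lagged and slope analyses. This is a wording change, unless the PHQ-9 is intended, in which case the survey description must include it.

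**Common origin.** Define the 3-month assessment in every arm as the same number of weeks after the same event, either randomisation or arm start. If arm start is chosen, say what marks it in the app arms. Bring the Study aims text and Assessment schedule into line, including which follow-ups the app arms complete. The cost is schedule wording and the timing of the survey invitations.

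### The later-outcome process analyses list symptom outcomes only as diagnostic classifications; under a yes/no cut this would cost about 8 to 31 points of power at 100 students, and the scores are already in hand

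*Combined protocol and SAP*

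**What the plan says.** The relevant text is in the process-analysis paragraphs of Statistical Analyses, under METHODS. The process assessments are "carried out every two weeks with students in the intervention arm over the 10 weeks of the intervention", so these analyses use the group CBT arm alone.

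The plan relates use of cognitive and behavioural skills (CSF and BSF), and individual PHQ-4 slopes on them, "with the outcomes at the end of the intervention and in the 3-month, and 6-month follow-ups". It then defines those outcomes by a closed list: academic attrition, "performance, and engagement along with diagnostic classifications based on the GAD-7, PHQ-9, and PCL". No symptom score is listed as an outcome at these three times.

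The first step of the process analyses, within treatment, does use a score: "Our interest will be in determining whether CSF and BSF predictor PHQ-9 scores and if these associations increase over time".

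Later sentences cover means, changes and slopes of skill use, and mediation, and refer to long-term outcomes without defining them again. The plan is also "especially interested in the possibility of nonlinearities that document the existence of important minimum engagement" thresholds.

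On size, students are "randomized in a 1:1 ratio to one of the four study arms", with a "target sample size of at least 400 students (i.e., a minimum of 100 students per intervention arm"). No cut-off, number of categories, link function, effect size or power is given for these analyses.

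**The concern.** Turning a symptom score into a class discards information. Two students on the same side of a cut count as equal however far apart they are, and a large change that stays on one side counts as none. Eligibility sets no symptom level, so some students may lie well away from any cut at both baseline and follow-up.

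The sample is small for the questions asked. One arm supplies about 100 students before loss to follow-up, and slopes, nonlinearity and mediation need more information than a single main effect. The plan gives no reason for using classes here when it uses scores during treatment. At stake is a real link between skill use and later symptoms going undetected for an avoidable reason.

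**Working it through.** **Plan's own figure.** Four arms of 100 give 4 × 100 = 400, which agrees with the stated target. There is no power figure to reproduce.

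**Inputs from the plan.** One arm, at least 100 students randomised to it.

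**Assumptions, none stated in the plan.**
- Two-sided 5% test, in line with the 95% intervals used elsewhere.
- Skill use and follow-up score bivariate normal, with correlation r of 0.2 to 0.4.
- Classification is one yes/no cut with a share p of 20-50% positive.
- n = 100, the minimum before loss to follow-up; n = 70 and 50 tried as well.

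**Power with the score (Fisher z).** Power ≈ Φ(atanh(r)·√(n − 3) − 1.96); the opposite tail is negligible. At r = 0.3 and n = 100: 0.3095 × √97 = 3.048, and Φ(3.048 − 1.96) = 86.2%.

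**Power with the class.** A cut at normal quantile h multiplies the correlation by φ(h)/√(p(1 − p)):
- p = 50%: 0.3989/0.5000 = 0.798
- p = 30%: 0.3477/0.4583 = 0.759
- p = 20%: 0.2800/0.4000 = 0.700

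The squares, 0.64, 0.58 and 0.49, are the relative efficiencies. At r = 0.3 and p = 20% the correlation becomes 0.210; 0.2131 × √97 = 2.099, and Φ(2.099 − 1.96) = 55.5%.

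**Results at n = 100.**

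| r | Score | Class, p = 50% | p = 30% | p = 20% | Loss (points) |
|---|---|---|---|---|---|
| 0.2 | 51.5% | 35.4% | 32.5% | 28.4% | 16.1 to 23.1 |
| 0.3 | 86.2% | 67.2% | 62.6% | 55.5% | 19.0 to 30.6 |
| 0.4 | 98.7% | 90.3% | 87.0% | 80.9% | 8.4 to 17.8 |

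A simulation comparing a Pearson test on the score with a logistic likelihood-ratio test on the class agrees. At r = 0.3 it gives about 87% against 69% (p = 50%) and 85% against 56% (p = 20%).

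**Smaller follow-up.** Over the same r and p, the loss is about 12 to 30 points at n = 70 and 9 to 32 at n = 50.

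**Outside these assumptions, n = 100.** The loss is 1.4 points at r = 0.5 with p = 50%, 4.4 at r = 0.1 with p = 50%, and 44.6 at r = 0.3 with p = 10%.

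**Several ordered categories.** With four categories holding 40/30/20/10% of students (assumed) and scored 0 to 3, the multiplier is 0.910. Power is then 44.1%, 78.7% and 96.4% at r = 0.2, 0.3 and 0.4, a loss of 7.4, 7.4 and 2.3 points. Other splits change this: 50/25/15/10% loses 9.7, 10.3 and 3.5 points.

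**The case against.** **The size rests on a reading the plan does not state.** The plan says classifications, not yes/no cuts, and gives neither a correlation nor a share positive. This stands. The 8 to 31 points are conditional, and with ordered categories the loss can be only a few points.

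**The list of classes is attached to one sentence.** This stands in part. Applying it to the mean, change, slope and mediation analyses is an inference from their reference to long-term outcomes. The threshold sentence names no outcome.

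**The basic association is already tested on a score during treatment.** True, so a real link would not necessarily be missed altogether. That step does not cover the end-of-intervention, 3-month and 6-month outcomes.

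**The analyses are exploratory, and classes match the remission outcomes used to compare arms.** Both points are fair. They argue for keeping the classes in the report, not for making them the only symptom outcome.

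**A stronger reading: the cut would create a false minimum engagement threshold.** A reader might infer this from the plan's interest in thresholds, but it is not supported. Take an exactly linear score relation with r = 0.4 and 20% cases. The risk at −2, −1, 0, +1 and +2 SD of skill use is 0.48, 0.32, 0.18, 0.09 and 0.04. It falls fastest at low engagement and flattens at high engagement, which is a plateau; a minimum threshold has the opposite shape. On the logit scale the steps are −0.70, −0.74, −0.82 and −0.93, so nothing flattens. In simulation at n = 100, a false quadratic term appeared in 6-9% of logistic fits, with no excess at 50% positive. A linear-probability model at r = 0.5 and 10-30% positive gave 17-25%, but the plan names no link.

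Total scores are not immune either. With 30% and 50% of students at the floor of the scale (assumed), false bends appeared in about 9% and 14% of runs at r = 0.4.

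**Conclusion.** The point holds in a limited, conditional form. At the three later times the plan names only classifications as symptom outcomes, gives no reason, and leaves unused scores that the same questionnaires supply.

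Under a yes/no cut, 20-50% positive and r = 0.2 to 0.4, the cost at 100 students is about 8 to 31 points of power. None of those conditions is in the plan. Outside them the loss ranges from about 1 to 45 points for a yes/no cut, and several ordered categories would usually lose much less than a single cut.

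No conclusion about false engagement thresholds follows. These are secondary, exploratory analyses, and the randomised comparison between arms is not affected. The change is worth making because it is cheap, not because the trial's main result depends on it.

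**What to change.** In the process-analysis text of Statistical Analyses, name the GAD-7, PHQ-9 and PCL total scores as the main symptom outcomes at the end of the intervention, 3 months and 6 months. Adjust each for the baseline score of the same scale where it is collected. State that the analyses referring to long-term outcomes use the same scores.

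Keep the diagnostic classifications as supportive results, with their cut-offs or categories defined, so that the link to the remission outcomes is retained. If nonlinearity is examined, do it on the scores and check for floor effects.

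The cost is a few lines of plan wording, with no new data, visits or students. The downside is that the main results are in scale points instead of case status; the retained classifications cover this.
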